10.5.2.2 Serious liver injury corresponding to Hy's Law

- ALT and TBIL normal at baseline:

ALT $> 3 \times$ ULN, with associated elevation in GLDH, without corresponding CK and/or troponin elevation, **together with** TBL $\geq 2 \times$ ULN, where no other reason, other than the investigational product, can be found to explain the combination of increases; eg, elevated ALP indicating cholestasis, viral hepatitis, or another drug.

- ALT or TBIL abnormal at baseline:

ALT $> 3 \times$ baseline or > 300 U/L (whichever occurs first), with associated elevation in GLDH, without corresponding CK and/or troponin elevation, **together with** TBL $\geq 2 \times$ ULN, or, if abnormal at baseline, $> 2 \times$ bsl, where no other reason, other than the investigational product, can be found to explain the combination of increases; eg, elevated ALP indicating cholestasis, viral hepatitis, or another drug.

If ALT is decreasing from baseline, nadir will be new baseline

For (potential) serious liver injury corresponding to Hy's law, the elevation in ALT must precede or be coincident with (ie, on the same day) the elevation in TBL, but there is no specified timeframe within which the elevations in ALT and TBL must occur.

10.5.3 Identification of cases of (potential) serious liver injury corresponding to Hy's law

In order to identify cases of (potential) serious liver injury corresponding to Hy's law, it is important to perform a comprehensive review of laboratory data for any subject who meets any of the following identification criteria in isolation or in combination:

ALT and TBIL normal at baseline:

- ALT $> 3 \times$ ULN, with associated elevation in GLDH
- TBL $\geq 2 \times$ ULN

ALT or TBIL abnormal at baseline:

- ALT $> 3 \times$ ULN, with associated elevation in GLDH, or, if abnormal at baseline, ALT $> 3 \times$ baseline or > 300 U/L (whichever occurs first), with associated elevation in GLDH,
- TBL $\geq 2 \times$ ULN, or, if abnormal at baseline, $> 2 \times$ bsl

If ALT is decreasing from baseline, nadir will be new baseline

When a subject meets any of the identification criteria, in isolation or in combination, the central laboratory will immediately send an alert to the investigator (also sent to sponsor study representative).

The investigator will also remain vigilant for any local laboratory reports where the identification criteria are met, where this is the case the investigator will:

- Notify the sponsor study representative
- Request a repeat of the test (new blood draw) by the central laboratory
- Complete the appropriate unscheduled laboratory case report form (CRF) module(s) with the original local laboratory test result

When the identification criteria are met from central or local laboratory results the investigator will without delay:

- Determine whether the subject meets criteria for (potential) serious liver injury corresponding to Hy's law (see Section 10.5.4.2) by reviewing laboratory reports from all previous visits (including both central and local laboratory results)

10.5.4 Follow-up

10.5.4.1 Criteria for (potential) serious liver injury corresponding to Hy's law Not Met

If the subject does not meet criteria for (potential) serious liver injury corresponding to Hy's law, the investigator will:

- Inform the study representative that the subject has not met criteria for (potential) serious liver injury corresponding to Hy's law.
- Perform follow-up on subsequent laboratory results according to the guidance provided in the study protocol.

10.5.4.2 Criteria for (potential) serious liver injury corresponding to Hy's law Met

If the subject does meet criteria for (potential) serious liver injury corresponding to Hy's law, the investigator will:

- Determine whether criteria for (potential) serious liver injury corresponding to Hy's law were met at any study visit prior to starting study treatment
- Notify the sponsor study representative who will then inform the study team

The medical monitor contacts the investigator, to provide guidance, discuss and agree an approach for the study subjects' follow-up and the continuous review of data. Subsequent to this contact the investigator will:

- Monitor the subject until liver biochemistry parameters and appropriate clinical symptoms and signs return to normal or baseline levels, or as long as medically indicated

- Investigate the etiology of the event and perform diagnostic investigations as discussed with the medical monitor. This includes deciding which the tests available in the Hy's Law lab kit should be used.
- Complete the Liver CRF Modules as information becomes available
- If at any time (in consultation with the medical monitor) the criteria for potential serious liver injury corresponding to Hy's law are met, report it as an SAE using standard reporting procedures

10.5.5 Review and Assessment of cases of (potential) serious liver injury corresponding to Hy's law

The instructions in this section should be followed for all cases where criteria for (potential) serious liver injury corresponding to Hy's law are met.

No later than 12 days after the biochemistry abnormality was initially detected, the medical monitor will contact the investigator in order to review available data and agree on whether there is an alternative explanation for meeting criteria for (potential) serious liver injury corresponding to Hy's law other than DILI caused by the investigational product. The medical monitor and Global Safety Physician will also be involved in this review together with other subject matter experts as appropriate. It is recommended to also consult with the hepatic SKG for review of these cases.

According to the outcome of the review and assessment, the investigator will follow the instructions below.

If there is an agreed alternative explanation for the ALT and TBL elevations, a determination of whether the alternative explanation is an AE will be made and subsequently whether the AE meets the criteria for a SAE:

- If the alternative explanation is **not** an AE, record the alternative explanation on the appropriate CRF
- If the alternative explanation is an AE/SAE, record the AE /SAE in the CRF accordingly and follow the sponsor's standard processes

If it is agreed that there is **no** explanation that would explain the ALT and TBL elevations other than the investigational product:

- Report an SAE (report term 'Drug-induced liver injury') according to the sponsor's standard processes.
 - The 'Medically Important' serious criterion should be used if no other serious criteria apply

- As there is no alternative explanation for the case of (potential) serious liver injury corresponding to Hy's law, a causality assessment of 'related' should be assigned

If, there is an unavoidable delay of over 12 days in obtaining the information necessary to assess whether or not the case meets the criteria for (potential) serious liver injury corresponding to Hy's law, then it is assumed that there is no alternative explanation until such time as an informed decision can be made:

- Report an SAE (report term 'Drug-induced liver injury') applying serious criteria and causality assessment as per above
- Continue follow-up and review according to agreed plan. Once the necessary supplementary information is obtained, repeat the review and assessment to determine whether criteria for (potential) serious liver injury corresponding to Hy's law are met. Update the SAE report according to the outcome of the review

10.6 Appendix 6 - Management of Liver Toxicity

In the setting of acute MI, transaminases used to monitor for liver toxicity (ALT and AST) can be elevated and of cardiac origin. [Table 14](#) describes actions to be taken according to ALT; GLDH; total bilirubin; and subject symptoms.

Table 14 Actions to be Taken According to ALT, Glutamate Dehydrogenase, Total Bilirubin

Treatment-emergent ALT		Treatment-emergent TBL	Liver Symptoms	Action
1	If normal at baseline: ALT > 3 x ULN, with associated elevation in GLDH, without corresponding CK and troponin elevation	Normal	None	Repeat ALT, AST, ALP, TBL, in 24-48 hours Follow-up for symptoms.
	If abnormal at baseline: ALT > 2 x baseline or > 200 U/L (whichever occurs first), with associated elevation in GLDH, without corresponding CK and troponin elevation If ALT is decreasing from baseline, nadir will be new baseline.	For patients with abnormal bsl, No change in baseline TBL		

Table 14 Actions to be Taken According to ALT, Glutamate Dehydrogenase, Total Bilirubin

Treatment-emergent ALT		Treatment-emergent TBL	Liver Symptoms	Action
2	If normal at baseline: ALT > 5 x ULN, with associated elevation in GLDH, without corresponding CK and troponin elevation	Normal	None	Interrupt study drug. Initiate close monitoring and workup for competing etiologies.
	If abnormal at baseline: ALT > 3 x baseline or > 300 U/L (whichever occurs first), with associated elevation in GLDH, without corresponding CK and troponin elevation If ALT is decreasing from baseline, nadir will be new baseline	For patients with abnormal bsl, No change in baseline TBL		Study drug can be restarted only if another etiology is identified and liver enzymes return to baseline.
3	If normal at baseline: ALT > 3 x ULN, with associated elevation in GLDH, without corresponding CK and troponin elevation	TBL > 2 x ULN	None	Interrupt study drug. Initiate close monitoring and workup for competing etiologies.
	If abnormal at baseline: ALT > 2 x baseline or > 200 U/L (whichever occurs first), with associated elevation in GLDH, without corresponding CK and troponin elevation If ALT is decreasing from baseline, nadir will be new baseline.	For patients with abnormal bsl, > 2 x bsl		Study drug can be restarted only if another etiology is identified and liver enzymes return to baseline.
4	If normal at baseline: ALT > 3 x ULN, with associated elevation in GLDH, without corresponding CK and troponin elevation	Normal or elevated	Severe fatigue, nausea, vomiting, right upper quadrant pain	Interrupt study drug. Initiate close monitoring and workup for competing etiologies.
	If abnormal at baseline:			Study drug can be restarted only if another etiology is identified and

Table 14 Actions to be Taken According to ALT, Glutamate Dehydrogenase, Total Bilirubin

Treatment-emergent ALT	Treatment-emergent TBL	Liver Symptoms	Action

ALT > 2 x baseline or > 200 U/L (whichever occurs first), with associated elevation in GLDH, without corresponding CK and troponin elevation
 
If ALT is decreasing from baseline, nadir will be new baseline
			liver enzymes return to baseline.

ALT = alanine transaminase; AST = aspartate transaminase; bsl = baseline; CK = creatine kinase; GLDH = glutamate dehydrogenase; TBL = total bilirubin; ULN = upper limit of normal.

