10.5.2 Definitions

10.5.2.1 Potential serious liver injury corresponding to Hy's Law

- ALT and total bilirubin (TBL) normal at baseline:
ALT $> 3 \times$ upper limit of normal (ULN), with associated elevation in glutamate dehydrogenase (GLDH), without corresponding CK and/or troponin elevation, **together with** TBL $\geq 2 \times$ ULN, at any point during the study following the start of study medication, irrespective of an increase in alkaline phosphatase (ALP).
- ALT or TBIL abnormal at baseline:
ALT $> 3 \times$ baseline or > 300 U/L (whichever occurs first), with associated elevation in GLDH, without corresponding CK and/or troponin elevation, **together with** TBL $\geq 2 \times$ ULN, or, if abnormal at baseline, $> 2 \times$ bsl, at any point during the study following the start of study medication, irrespective of an increase in alkaline phosphatase (ALP).

If ALT is decreasing from baseline, nadir will be new baseline

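### Table 14 lists no action for an asymptomatic subject whose ALT qualifies and whose bilirubin is raised but not above 2 x, so a mandatory dose interruption lapses as bilirubin rises

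*Protocol*

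**What the plan says.** Protocol Section 4.1.7 sends the reader to Section 10.6 for liver actions. All four rows of Table 14 require raised GLDH without matching CK and troponin elevation. They differ as follows.

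- **Row 1.** ALT > 3 x ULN (abnormal baseline: > 2 x baseline or > 200 U/L), TBL normal or unchanged from an abnormal baseline, no symptoms. Action: "Repeat ALT, AST, ALP, TBL, in 24-48 hours", plus follow-up for symptoms.
- **Row 2.** "If normal at baseline: ALT > 5 x ULN, with associated elevation in GLDH, without corresponding CK and troponin elevation" (abnormal baseline: > 3 x baseline or > 300 U/L), same TBL condition as row 1, no symptoms. Action: interrupt, monitor closely and work up other causes. The restart condition is: "Study drug can be restarted only if another etiology is identified and liver enzymes return to baseline".
- **Row 3.** ALT as in row 1, TBL > 2 x ULN (abnormal baseline: > 2 x baseline), no symptoms. Action as in row 2.
- **Row 4.** ALT as in row 1, TBL "Normal or elevated", liver symptoms required. Action as in row 2.

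Appendix 5 (Section 10.5.2.1) defines potential Hy's law with a slightly different bilirubin limit for a normal baseline: "TBL $\geq 2 \times$ ULN, at any point during the study following the start of study medication".

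**The concern.** A stopping rule for liver safety should not relax as the liver signal worsens. Rows 1 and 2 stop at normal (or unchanged) bilirubin and row 3 starts above 2 x. An asymptomatic subject in between has no listed action. In the row 2 ALT band, someone with the same ALT and a higher bilirubin loses the mandatory interruption and the restart condition attached to it. In the lower ALT band the loss is smaller: the repeat tests and symptom follow-up of row 1.

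There is also a boundary mismatch. For a normal TBL baseline, row 3 uses strictly above 2 x ULN, while Appendix 5 uses 2 x ULN or above. An asymptomatic case at exactly 2.0 x ULN can be potential Hy's law and still match no interruption row. For an abnormal TBL baseline both appendices use > 2 x baseline and agree.

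**Working it through.** **Mapping the rows.** Take an asymptomatic subject who meets the GLDH and CK/troponin conditions. TBL is in multiples of ULN (normal TBL baseline) or of baseline (abnormal TBL baseline).

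| TBL multiple | Lower ALT band (e.g. 4 x ULN) | Row 2 ALT band (e.g. 6 x ULN) |
|---|---|---|
| 1.0 | row 1: repeat tests | rows 1 and 2: interrupt |
| 1.01 | no row | no row |
| 1.5 | no row | no row |
| 2.0 | no row | no row |
| 2.01 | row 3: interrupt | row 3: interrupt |
| 2.5 | row 3: interrupt | row 3: interrupt |

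The pattern is the same for normal and abnormal baselines, including a mix of the two for ALT and TBL, if the TBL column is read by the TBL baseline. For an abnormal TBL baseline I take any rise as a change, because the table gives no numeric limit. With symptoms, row 4 applies at every TBL and there is no gap.

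**Whether other sections supply the dosing action.**

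- Section 4.1.7 lets the investigator or medical monitor stop drug for safety, on judgement, and points back to Section 10.6.
- Section 4.3.4 leaves follow-up of abnormal results to the investigator.
- Section 10.5.3 has identification criteria that work in isolation; when one is met, "the central laboratory will immediately send an alert to the investigator". A review of laboratory data follows. The ALT criterion covers the whole row 2 band and, for a normal ALT baseline, the row 1 band too. For an abnormal ALT baseline it starts at > 3 x baseline or > 300 U/L, so the row 1 range below that has no ALT alert.
- Section 10.5.4.1, when Hy's-law criteria are not met, says: "Perform follow-up on subsequent laboratory results according to the guidance provided in the study protocol". For dosing, that leads back to Table 14.
- Section 10.5.4.2, when they are met, says: "The medical monitor contacts the investigator, to provide guidance, discuss and agree an approach for the study" subject's follow-up. It states no interruption.

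**Reach.** Cohort B is dosed on Days 1, 3, 10, 17, 24 and 31; Cohort A finishes on Day 3 (Section 3.1.2). Table 9, as extracted, schedules chemistry in the dosing phase on Days 3, 17 and 31. Doses still to come:

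- after Day 3: Days 10, 17, 24, 31 = 4
- after Day 17: Days 24, 31 = 2 (3 if the result is back before the Day 17 dose)
- after Day 31: 0 (1 if the result is back before the Day 31 dose)

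Day 3 is about 48 hours after Dose 1. If CK and troponin are still raised then (an assumption), Table 14 does not apply to that sample, and the reach is mainly the Day 24 and Day 31 doses.

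Row 1 would repeat tests within 24-48 hours. For a Day 17 result in the gap, the next scheduled chemistry is Day 31: 31 - 17 = 14 days. With the +/- 1 day windows this is 30 - 18 = 12 to 32 - 16 = 16 days, with the Day 24 dose in between.

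**The case against.** The strongest reply is that nothing in the table is false. It is silent, and silence does not mean carry on dosing. An investigator told to interrupt at ALT > 5 x ULN with normal bilirubin would hardly continue when bilirubin is raised as well. The range is also supervised: alerts go to investigator and sponsor, Section 5.1 makes the investigator responsible for following up laboratory abnormalities and provides a 24-hour hotline, and Section 4.1.7 allows drug to be stopped. All of this stands and keeps the point minor. None of it sets a dosing action, and the mandatory rule still drops out where the signal is worse.

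A second reply is that the table may intend two bilirubin states, with normal meaning anything short of the row 3 trigger. Row 4 names elevated separately from normal, and the abnormal-baseline wording in rows 1 and 2 asks for no change at all, so this reading does not hold. It is fair that the lower edge of the gap for an abnormal baseline has no number in the protocol. That blurs the edge but does not close the gap.

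It is also fair that the mismatch at exactly 2.0 x ULN concerns one boundary value, already handled through the medical monitor if Hy's-law criteria are met. The reach figures rest on an extracted table whose columns may have shifted, and unscheduled or local tests could shorten the 14-day interval.

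**Conclusion.** The concern holds. Table 14 has no row for an asymptomatic subject with a qualifying ALT and TBL above 1 x and up to 2 x ULN (or an abnormal baseline). In the row 2 ALT band the written rule runs interrupt, no listed action, interrupt as bilirubin rises. The normal-baseline limits in row 3 and Appendix 5 also differ at exactly 2 x ULN.

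Severity is minor. Practical harm is limited by the alert, the investigator's discretion and medical-monitor involvement. Exposure is confined to later Cohort B doses, although under Section 4.2.1.1 item 2 all new subjects enter Cohort B. No endpoint, analysis population or error rate is affected. The gap itself follows from the table's wording alone. The reach depends on the extracted Table 9 schedule and on the Day 3 CK/troponin assumption.

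**What to change.** Amend three rows of Table 14:

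1. **Row 2:** at its existing ALT thresholds, apply the interruption, monitoring, work-up and restart condition whatever the TBL. This alone removes the reversal.
2. **Row 1:** at its lower ALT thresholds, extend the repeat tests and symptom follow-up to any TBL that does not reach the row 3 threshold.
3. **Row 3:** for a normal TBL baseline, use TBL >= 2 x ULN, matching Section 10.5.2. Leave > 2 x baseline for an abnormal TBL baseline.

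With these edits and normal baselines, ALT 6 x ULN gives interruption at every TBL. ALT 4 x ULN gives repeat tests at TBL 1.0 and 1.5 x ULN and interruption at 2.0 and 2.5.

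The cost is a wording change in one appendix table. Scheduled visits and analyses stay as they are. The only added work is the existing row 1 repeat test for subjects now in the gap, and the interruption work-up for those in the row 2 band or at exactly 2 x ULN.

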Table 2.1	Primary Objective and Associated Endpoint	6
Table 2.2	Secondary Objectives and Associated Endpoints	6
Table 2.3	Exploratory Objectives and Associated Endpoints.....	7
Table 3.1	Analysis Populations.....	12
Table 3.2	Post-randomization Analysis Subgroups	15

LIST OF FIGURES

Figure 2.1	Overall Study Schema.....	9
Figure 2.2	Study Flow Diagram for Cohort A: 2-Dose Regimen	9
Figure 2.3	Study Flow Diagram for Cohort B: 6-Dose Regimen	10
Figure 4.1	Predictive power against observed interim relative infarct size reduction when 30% of the Primary Efficacy Analysis Population is enrolled and complete their final study visit.....	24
Figure 4.2	Predictive power against observed interim ejection fraction increase when 30% of the Primary Efficacy Analysis Population is enrolled and complete their final study visit.....	24

List of Abbreviations

Abbreviation or Specialized Term	Definition
ACS	acute coronary syndrome
ADA	anti-drug antibody
AE	adverse event
ALT	alanine transaminase
apoA1	apolipoprotein A1
apoB	apolipoprotein B
AST	aspartate aminotransferase
AUC	area under the concentration-time curve
AUC _{0-∞}	area under the concentration-time curve from 0 to infinity
AUC _{0-72h}	area under the concentration-time curve from 0 to 72 hours
BP	blood pressure
CAD	coronary artery disease
CE	cholesteryl ester
CETP	cholesteryl ester transfer protein
CHD	coronary heart disease
C _{max}	maximum plasma concentration
CMR	cardiovascular magnetic resonance
CTA	computed tomography angiography
CV	cardiovascular disease
ECG	electrocardiogram
eCRF	electronic case report form
EDC	electronic data capture
EF	ejection fraction
eGFR	estimated glomerular filtration rate
FAAN	Food and Allergy Anaphylaxis Network
FC	free cholesterol
HDL	high-density lipoprotein
HDL-C	high-density lipoprotein-cholesterol
HDL-CE	High-density lipoprotein-cholesterol ester
HF	heart failure
ICD	implantable cardioverter-defibrillator
ICF	informed consent form
ICH	International Council for Harmonisation
IDMC	Independent Data Monitoring Committee
IEC	Independent Ethics Committee
IRB	Institutional Review Board
IV	intravenous(ly)
IXRS	Interactive response system

Abbreviation or Specialized Term	Definition
LAD	left anterior descending artery
LCAT	lecithin-cholesterol acyltransferase
LDL	low-density lipoprotein
LDL-C	low-density lipoprotein-cholesterol
LV	left ventricle
MACE	major adverse cardiac events
MedDRA	Medical Dictionary for Regulatory Activities
MI	myocardial infarction
MR	magnetic resonance
MRI	magnetic resonance imaging
nAb	neutralizing antibody
NCPV	non-calcified plaque volume
NO	nitric oxide
NOAEL	no-observed-adverse-effect-level
pPCI	primary percutaneous coronary intervention
PD	pharmacodynamics
PK	pharmacokinetics
PT	preferred term
RCT	reverse cholesterol transport
rhLCAT	recombinant human lecithin-cholesterol acyltransferase
SAE	serious adverse event
SID	subject identification
SOC	system organ class
STEMI	ST segment elevation myocardial infarction
sWFI	sterile water for injection
TEAE	treatment-emergent adverse event
TESAE	Treatment-emergent serious adverse event
TFG	TIMI flow grade
TIMI	Thrombolysis in Myocardial Infarction
ULN	upper limit of normal
USA	United States of America

1 INTRODUCTION

This document describes the statistical analysis for protocol D5780C00007, A Randomized, Placebo controlled Phase 2b Study to Evaluate the Safety and Efficacy of MEDI6012 in Acute ST Elevation Myocardial Infarction. An overview of the study design and objectives are provided in Section 2 (pg. 6). Details for statistical methods and general conventions are provided in Section 3 (pg. 11). In addition, a set of table templates and specifications will be included in a statistical programming plan (SPP) to complement this document.

2 STUDY OVERVIEW

2.1 Study Objectives

2.1.1 Primary Study Objective(s)

The primary objective and associated endpoint is presented in Table 2.1.

Table 2.1 Primary Objective and Associated Endpoint

Type	Objective	Endpoint
Efficacy	To evaluate the effect of MEDI6012 [REDACTED]	Infarct size as a percentage of LV mass measured on delayed-enhanced CMR imaging 10-12 weeks post-MI compared to placebo.

CMR = cardiovascular magnetic resonance; LV = left ventricle; MI = myocardial infarction.

